## **E. Study Procedures**

**Session procedures:** Before the test sessions, smokers will be required to abstain from smoking for 10 h, which will be verified by expired air CO levels  $\leq 8$  ppm (Benowitz et al. 2002). Subjects will be asked to refrain from consuming alcoholic beverages and drugs during study participation, which will be verified by a urine drug quick test. If results indicate non-compliance with these study procedures, subjects will be discharged from the study. Subjects will be instructed to drink their typical amount of caffeinated beverages in the morning to minimize caffeine withdrawal, which could confound the study measures. Subjects will be instructed not to eat for four hours before the lab sessions to reduce the chance of vomiting. A light lunch will be provided at the end of each experimental session.

**Medical monitoring:** Subjects will be given a thorough physical examination prior to entry in the study. For nicotine administration sessions, a physician will be present and subjects will be attached to a cardiac monitor as well as a blood pressure and heart rate monitoring device. An IV catheter will be in place throughout the session. Subjects will be administered nicotine only if the systolic blood pressure is  $<150$  mmHg and heart rate is  $<100$  beats/minute. Subjects will be terminated from the study if the blood pressure at any time is  $>170/110$  mm Hg, the heart rate is  $>120$  beats/min, or if they develop signs and symptoms compatible with nicotine toxicity. Subjects will remain in the laboratory for at least an hour after the last nicotine administration. These procedures have been developed as part of our IND for IV nicotine.

TABLE 1. SCHEDULE OF EVENTS: EXPERIMENTAL SESSION\*

Minutes	Time point	Measures and Events
0 Min	1	HR/BP, DEQ, IV nicotine or saline administration A (sampling) CO, HR/BP, EKG, M
1 Min	2	HR/BP, DEQ
2 Min	3	HR/BP,
3 Min	4	HR/BP, DEQ
5 Min	5	HR/BP, DEQ
15 Min	6	HR/BP, DEQ IV nicotine or saline administration B
16 Min	7	HR/BP, DEQ
17 Min	8	HR/BP
18 Min	9	HR/BP, DEQ
20 Min	10	HR/BP, DEQ
30 Min	11	HR/BP, DEQ IV Choice Sampling Option 1
31 Min	12	HR/BP, DEQ
32 Min	13	HR/BP
33 Min	14	HR/BP, DEQ
35 Min	15	HR/BP, DEQ
45 Min	16	HR/BP, DEQ IV Choice Sampling Option 2
46 Min	17	HR/BP, DEQ
47 Min	18	HR/BP
48 Min	19	HR/BP, DEQ
50 Min	20	HR/BP, DEQ
60 Min	21	HR/BP DEQ IV sampling Option 3
61 Min	22	HR/BP, DEQ
62 Min	23	HR/BP
63 Min	24	HR/BP, DEQ
65 Min	25	HR/BP, DEQ
75 Min	26	HR/BP, DEQ IV sampling Option 4
76 Min	27	HR/BP DEQ
77 Min	28	HR/BP,
78 Min	29	HR/BP, DEQ
80 Min	30	HR/BP, DEQ
90 Min	31	HR/BP, DEQ IV sampling Option 5

91 Min	32	HR/BP DEQ
92 Min	33	HR/BP,
93 Min	34	HR/BP, DEQ
95 Min	35	HR/BP, DEQ
105 Min	36	HR/BP, DEQ IV sampling Option 6
106Min	37	HR/BP DEQ
107Min	38	HR/BP,
108 Min	39	HR/BP, DEQ
110 Min	40	HR/BP, DEQ
120 Min	41	HR/BP DEQ IV sampling Option 7
121 Min	42	HR/BP DEQ
122 Min	43	HR/BP,
123 Min	44	HR/BP, DEQ
125 Min	45	HR/BP, DEQ
135 Min	46	HR/BP DEQ IV sampling Option 8
136 Min	47	HR/BP DEQ
137 Min	48	HR/BP,
138 Min	49	HR/BP, DEQ
140 Min	50	HR/BP, DEQ
150 Min	51	HR/BP DEQ IV sampling Option 9
151 Min	52	HR/BP DEQ
152 Min	53	HR/BP,
153 Min	54	HR/BP, DEQ
155 Min	55	HR/BP, DEQ
165 Min	56	HR/BP DEQ IV sampling Option 10
166 Min	57	HR/BP DEQ
167 Min	58	HR/BP,
168 Min	59	HR/BP, DEQ
170 Min	60	HR/BP, DEQ
180-240 Min	61	HR/BP, DEQ, EKG, SCF M-NWSC, BQSU, PANAS, SNACK and Discharge

\*Same measure will be obtained following saline and each nicotine administration. For brevity, only the measures after saline are shown.

Abbreviations: CO: Alveolar carbon monoxide, HR/BP: Heart rate/Blood pressure; EKG: Electrocardiogram; SCF: Symptom Checklist form; M-NWSC: Minnesota Nicotine Withdrawal Symptom Checklist; BQSU: Brief Questionnaire of Smoking Urges; PANAS: Positive and Negative Affective Schedule; DEQ: Drug Effects Questionnaire.

Experimental sessions: The schedule of events during the experimental sessions is shown in Table 1. Before the session begins, subjects will have an IV catheter placed and the baseline measures will be taken. Subjects will begin NSA as described below.

Nicotine self-administration procedure:

Apparatus: Saline and nicotine will be administered with two separate infusion pumps, which will be prepared with IV infusion bags randomly labeled as Drug A or B by the research pharmacist. Both the researchers and the subjects will be blind to the randomization. The infusion pumps will deliver saline and nicotine at a precise rate and volume.

Procedure: The NSA procedure will consist of two phases: Sampling and Nicotine Choice.

Sampling: In each of the five test sessions, subjects will be randomly assigned to one of the five doses of nicotine: 0.0125, 0.025, 0.05, 0.1 and 0.2 mg/70 kg. Subjects will first receive saline and the assigned nicotine dose in a randomized order and double-blind fashion. Subjects will be informed that they will be receiving drug A or B, which may be nicotine or saline. This procedure will allow subjects to sample the nicotine and saline that will be available during that session. In addition, subjective and physiological responses to the sample nicotine dose and saline will be assessed.

Nicotine Choice procedure: Beginning 15 minutes after the sampling phase is completed, subjects will be asked to make a choice between drug A or B every 15 minutes for a total of ten choices over 150 minutes. The drug chosen by the subjects will be immediately delivered with the infusion pump over 30 sec in 5 ml of saline. This choice procedure has been used in our IV nicotine self-administration study as well as in many previous studies with various drugs of abuse (Sofuoglu et al. 1999, 2000, 2001; 2009c). One particular advantage of this model, compared to the ad lib models used in previous IV nicotine self-administration studies (Harvey et al. 2004; Rose et al. 2003), is the ability to control amount of nicotine delivered without interfering with the self-administration behavior.

## **12. Data analysis methods:**

Data analyses: The primary analyses will be intent-to-treat and will include all available data on subjects who complete at least one test day. Mixed-effects models will be used to test the study hypotheses. These models allow for different numbers of observations per subject, use all available data on each subject, and are unaffected by randomly missing data. They also provide flexibility in modeling the correlation structure of the data. All data will be checked for normality and transformations will be applied as necessary. Significance level of 0.05 will be used for the main hypotheses and Bonferroni correction will be applied for post-hoc tests and secondary analyses.

Specific Aim #1: Aim #1: To assess the threshold reinforcing dose and dose-effect curve for IV NSA at low doses in young adult LITS. Hypothesis #1A: The threshold reinforcing doses for IV NSA will be between 0.0125 to 0.05 mg/70 kg. Hypothesis #1B: The dose-effect curve for NSA will differ between males and females with relatively flat curve in female smokers.

**Aim #1 Analysis:** The reinforcing effects of nicotine will be determined by the number of IV NSAs in each session, ranging from 0 to 10. The threshold dose for NSA will be determined by the lowest dose of nicotine for which the number of NSAs is significantly greater than those for placebo (saline) (i.e., proportion of NSA significantly higher than 0.5). For assessing the dose-response relationship, the parameters of interest will be the slope and shape of the dose-response curve. The slope indicates the degree to which self-administration changes with an increase in nicotine dose (in other words, sensitivity of NSA to changes in nicotine dose).

The analysis of Aim #1 will conducted in several steps. First, we will use descriptive statistics and figures to summarize the data. In particular, the number of NSAs for each dose of nicotine will be plotted individually, for the entire sample, and for male vs. female and smokers. This step will allow a visual inspection of both individual and group differences for estimating the threshold dose and the shape of the dose-response curve for nicotine reinforcement. Second, we will fit mixed effects logistic regression models with the proportion of NSAs per session (out of 10) as the dependent variable, dose as a fixed categorical predictor and subject as a random effect. This approach allows us to take into account the correlations between repeated observations on the same individual and to estimate individual deviations from the overall group thresholds.

It also does not assume a specific form of the dose-response relationship and allows us to use all available data on a subject in the unlikely event that a subject fails to complete a session. If a subject fails to complete a session, the total possible number of self-administrations for this subject and session will be adjusted.

We expect to observe a significant dose effect and will compare the proportion of NSAs at each dose to 0.5 across subject groups. The lowest nicotine dose that has a significantly higher proportion of NSA than 0.5 will be selected as the threshold dose (Hypothesis 1A). To assess the dose-response relationship in the preference for nicotine, polynomial effects of dose (linear, quadratic, cubic) and change-point linear models will be tested in the mixed effects logistic regression model. We anticipate that there will be a significant linear relationship between dose and response rate at lower doses with flattening of the relationship at higher doses. We will use the slope of the dose effect to assess the linear dose effect. Alternative non-linear dose response relationships will be considered if residual plots reveal significant deviations of the models from linearity. Gender differences in the shape of the curve for NSA will be examined in the logistic regression model by including gender main effect and its interactions with dose (Hypothesis 1B). Significant interactions between the group factors and dose will be considered supportive of systematic group differences in the dose-response relationships between groups. If significant interactions are observed, then separate thresholds and curves will be estimated within each subject group.

**Specific Aim #2:** To assess the threshold and dose-effect curve for the positive and negative/aversive subjective effects of IV nicotine at low doses and its relationship to nicotine reinforcement. Hypothesis #2 A: The threshold for the positive effects will be between 0.0125 to 0.1 mg/70 kg, for the negative/aversive effect it will be  $\geq 0.1$  mg/70 kg. Hypothesis #2B: Nicotine reinforcement will be positively correlated with the positive and negatively correlated with the negative/aversive subjective effects of IV nicotine.

**Aim 2 Analysis:** The subjective-positive effects of nicotine which will be determined by the main dependent variables of scores on the "like the drug" and "want more drug" items of the Drug Effects Questionnaire, ranging from 0 to 100. The negative aversive effects of nicotine will be determined by the "dislike the drug" and "lightheaded/dizzy" item of the DEQ. The analysis for Specific Aim #2A will be similar to the analysis described for Specific Aim #1A except that the dependent variables will be continuous and thus we will use random effects linear regression. Gender effects will be explored also as outlined for Specific Aim #1B. Prior to analysis, we will also assess the distribution of the DEQ items and apply transformations as necessary. Furthermore, the mean ratings at each dose will be compared to 0. To assess the

relationship between nicotine reinforcement and positive subjective effects, and between nicotine reinforcement and negative subjective effects (Specific Aim #2B), we will use mixed effects models with the proportion of NSAs per session as the dependent variable, positive (negative) subjective effects in response to the sample dose as the main predictor of interest (in separate models for positive and negative effects). Nicotine dose, gender and the interactions among subjective effects, dose and gender will also be assessed. Non-significant interactions will be dropped from the models via backward elimination subject to the constraint that the models will be hierarchically well-formulated at each step. Statistically significant associations between subjective effects and NSA across doses and gender are expected but we will also explore whether these relationships vary by gender and dose.

**Exploratory Aim #1:** To examine the association between baseline 3HC/cotinine ratio and nicotine reinforcement threshold. To test this hypothesis, correlation analysis including 3 HC/cotinine ratio and nicotine reinforcement threshold will be performed in the total sample as well as in subgroups (male vs. female smokers).

**Rationale for sample size:** Power for Specific Aims 1 and 2 is based on our preliminary studies comparing nicotine doses of 0.1, 0.2, 0.3 and 0.4mg to saline (34). We consider a difference between 50% (half of infusions in favor of nicotine) and 67% (two-thirds in favor of nicotine) as clinically meaningful. With our sample of 72 subjects we can detect such a proportion (67%) as statistically different from 50% with 80% power assuming two-sided test and alpha=0.05 (Specific Aim 1). Also with our sample of 72 subjects, we can detect medium effects ( $d'=0.34$ ) for the threshold tests on “good effects” and “drug liking” under the same assumptions (Specific Aim 2).

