## **B. Medical Monitoring and Safety**

Subjects will be given a thorough physical examination prior to entry in the study. For nicotine administration sessions, a physician will be present and subjects will be attached to a cardiac monitor as well as a blood pressure and heart rate monitoring device. An IV catheter will be in place throughout the session. Subjects will be administered nicotine only if the systolic blood pressure is <150 mmHg and heart rate is <100 beats/minute. Subjects will be terminated from the study if the blood pressure at any time is >170/110 mm Hg, the heart rate is >120 beats/min, or if they develop signs and symptoms compatible with nicotine toxicity. Subjects will remain in the laboratory for at least an hour after the last nicotine administration. These procedures have been developed as part of our IND for IV nicotine.

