- All paper documents will be locked in an approved file cabinet with only members of the research team having access.

Electronic:

- All information in electronic form will be stored on VA servers behind the VA firewall.
- All portable media will meet or exceed FIPS 140-2 compliance and encryption. And will be approved in writing by the Information Security Officer.

The location(s) where information will be stored is (are) Building 35, rooms 19 and 39

The people or agencies that will have access to the information are the study investigators.

No information related to this research will be released to any third party or disclosed outside of the VHA – except as required or permitted by law.

Research records will have identifiers removed and will be stored with a code number linked to subjects. The code will not be derived from any personal identifiers. The key to the code will be kept in a locked file cabinet, located in Bldg 35, room 19. Subjects' identity will not be revealed in any reports or publications resulting from this study.

**17. Location of Study:** This study will be conducted in Ward G9W (the Biostudies Unit) located in Building 1 at the West Haven VA Medical Center.

**18. Payment:** Subjects will be paid \$30 for participating in the screening and \$130 for each of the 5 lab sessions and \$20 for transportation for each of the 5 test sessions. If the subjects choose to terminate a session prematurely, or a session is terminated early for medical reasons, they will receive full payment for that day. If they become ineligible to continue in the study due to non-compliance with study procedures, they will only be paid for the portions of the study in which they have participated. Subjects may also earn \$20 for referring people they know who also smoke cigarettes and are eligible for study participation. A contingency payment of \$20 will also be given for transportation for a visit that wasn't fulfilled in the outlined time frame within the protocol. Subjects may be paid up to \$780 if all parts of the study are completed.

**19. Funding Source:** An RO1 grant from NIDA (pending).

**20. Duration:** The new study design will take approximately 3 years to complete.

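### The primary set is labelled intent-to-treat but leaves out any subject who never completes a test day, including every safety termination in the first session

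*Combined protocol and SAP*

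**What the plan says.** The opening paragraph of section 12 (Data analysis methods) defines who is analysed: "The primary analyses will be intent-to-treat and will include all available data on subjects who complete at least one test day". It adds that mixed models "use all available data on each subject, and are unaffected by randomly missing data".

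The Aim #1 Analysis in the same section says that the chosen model "allows us to use all available data on a subject in the unlikely event that a subject fails to complete a session", and gives the counting rule: "If a subject fails to complete a session, the total possible number of self-administrations for this subject and session will be adjusted".

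Section 11.B (Medical Monitoring and Safety), repeated in 11.E and 14, provides for permanent removal during a session: "Subjects will be terminated from the study if the blood pressure at any time is >170/110 mm Hg", for a heart-rate limit, "or if they develop signs and symptoms compatible with nicotine toxicity". Section 18 (Payment) also foresees early endings: "If the subjects choose to terminate a session prematurely, or a session is terminated early for medical reasons".

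The documents do not define what completing a test day means. They name no second analysis set and plan no sensitivity analysis for subjects without a completed day.

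**The concern.** An intent-to-treat set should not depend on what happens after randomisation. This one requires the subject to have finished a day of dosing. One way of failing to finish is termination for blood pressure, heart rate or signs of toxicity, so the exclusion is not plainly random. The plan's reassurance about missing data covers only data missing at random.

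Two results are exposed. Hypothesis 2A places the aversive threshold at or above 0.1 mg/70 kg, and the rule can remove aversive ratings from the subjects who reacted worst. Hypothesis 1A takes as threshold the lowest dose with a nicotine-choice proportion significantly above 0.5, so selection at one dose bears on it directly.

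**Working it through.** **1. Who is in and who is out.**

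| Subject | Completed day | In primary set | Partial session used |
|---|---|---|---|
| Ends session 1 early, completes a later day | yes | yes | yes, adjusted denominator |
| Completes session 1, terminated in session 2 | yes | yes | yes, adjusted denominator |
| Terminated for safety in session 1 | no | no | no |
| Withdraws for good in session 1 | no | no | no |

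The order of sessions is not the criterion. What counts is whether the subject completes any day at all.

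**2. What data are lost.** In Table 1 the sample infusions are at 0 and 15 minutes, DEQ ratings follow each, and the choices run from 30 to 165 minutes. A subject stopped after the choice at 60 minutes has both sets of sample ratings and 3 choices. A subject stopped before 30 minutes has sample ratings only.

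**3. The plan's own figures.** Section 12 gives 72 subjects and 80% power for 67% against 50%, two-sided alpha 0.05. With one binary outcome per subject, N = [(1.96×0.5 + 0.842×√(0.67×0.33))/0.17]² = 65.5. With continuity correction, 65.5/4 × [1 + √(1 + 2/(65.5×0.17))]² = 71.2, rounded up to 72. That reproduces the stated size. The exact binomial power at 72 is 82.6%. For Aim 2, a one-sample t test with d = 0.34 and n = 72 has 81.2% power. The 72 are target completers, so the definition of the set changes neither figure.

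**4. Size for Aim 1.** The documents give no rate of first-session stops. Assumptions: 72 retained subjects with proportion 0.60 over 10 choices at one dose; four excluded subjects, all at that dose, with proportion 0.30 over 3 choices; within-subject correlation 0.3.

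- Standard error: √(0.25 × (1 + 9×0.3)/(72×10)) = √(0.25×3.7/720) = 0.036.
- Weighted by choices: 0.30 × 12/(720 + 12) = 0.005.
- Weighted by m/(1 + 0.3(m − 1)): 10 choices give 10/3.7 = 2.703 and 3 choices give 3/1.6 = 1.875. Shift = 0.30 × 7.5/(7.5 + 72×2.703) = 0.30 × 7.5/202.1 = 0.011.
- Equal weight per subject, an upper figure: 0.30 × 4/76 = 0.016.

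The first two shifts are 0.14 and 0.31 of a standard error. Four stops at one dose is already many. If first-session doses were balanced, 76/5 = 15.2 subjects would start at each dose, and 4/15.2 is 26%.

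Range with excluded subjects' preference between 0 and 0.5, showing what 0.60 becomes when they are added back:

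| Stops at the dose | Weighted by choices | Equal weight |
|---|---|---|
| 1 | 0.598–0.600 | 0.592–0.599 |
| 5 | 0.588–0.598 | 0.561–0.594 |
| 10 | 0.576–0.596 | 0.527–0.588 |

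**5. Size for Aim 2.** A subject stopped after the sampling phase has all the scheduled sample-dose ratings for that session and would count about as much as any other. Four such subjects at one dose shift the mean by 4/76 = 0.053 of whatever difference separates them from the rest. If that difference were one standard deviation (an assumption), the shift would be 0.053 SD against a standard error of 1/√72 = 0.118 SD, a ratio of 0.45. The documents give no figure for the difference.

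**The case against.** The strongest reply is that the two rules do not conflict. One decides which subjects enter. The other decides how an incomplete session of an included subject is counted. Both can be applied together, and that stands: a reader might infer a formal contradiction, but the text shows only a rationale that is not carried through, together with a loose label.

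A reader might also infer that everyone stopped in the first session is dropped. The documents do not support this. Section 18 pays in full for a session ended early and does not say that participation ends, so such a subject can return, complete a later day and keep the partial session.

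A third tempting reading is that preference at the higher doses will be overstated. Nothing in the documents ties first-session stops to dose or to low preference; a subject stopped for heart rate may have been choosing nicotine. The documents point to rarity. The Aim #1 Analysis calls incomplete sessions unlikely, and section 13 reports no adverse events from intravenous nicotine in more than 100 smokers. The preliminary studies call 1.5 to 6.0 mcg/kg well tolerated, while the top dose here is about 2.8 µg/kg. They found aversive effects above saline only at 0.3 mg, higher than any dose in this trial.

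Finally, requiring at least one choice is itself a condition after randomisation. That limits the remedy for Aim 1, because a subject stopped during sampling has no choice to analyse. It does not defeat the remedy: that subject's sample ratings are recovered for Aim 2.

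**Conclusion.** The point holds in a limited form. The primary set is not intent-to-treat: it excludes every subject with no completed test day, which includes all safety terminations and permanent withdrawals during session 1, and it discards data that the plan's own counting rule could use. The reason for exclusion may be drug-related.

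The clearest exposure is the sample-dose DEQ ratings for the Aim 2 aversive threshold; its size cannot be fixed from the documents. For Aim 1 the shift is probably small, about 0.005 to 0.011 at one dose against a standard error of about 0.036. That rests on four stops at one dose, 3 choices each, preferences of 0.30 against 0.60 and a correlation of 0.3, none of which the documents give. Upward bias in preference is plausible, not shown. Sample size and power are not affected. The case for a change rests on the label and the avoidable loss of data, not on a large bias.

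**What to change.** Replace the entry condition in the opening paragraph of section 12. The primary set becomes all randomised subjects with at least one recorded A/B choice (Aim 1) or at least one post-sample DEQ rating (Aim 2). Partial sessions enter with the adjusted denominator that the Aim #1 Analysis already provides. Note that the Hypothesis 2B model needs both a rating and a choice, so subjects with ratings alone contribute to Hypothesis 2A only.

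Call this a modified intent-to-treat set, because subjects stopped before the first choice still give no Aim 1 data. Report the number of first-session stops by dose and reason, so that a reader can judge what remains missing.

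The cost is two or three sentences and one small table. The ratings and choices are already scheduled in Table 1. No extra subjects are needed, the target of 72 completers stays, and no clinical rule changes.

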## **11. Research Plan:**

### **A. Overview**

This will be a double-blind, placebo-controlled study, with 72 LITS (36 male and 36 female smokers) participating in five experimental sessions. All sessions will be conducted following overnight abstinence to control for recent nicotine intake. The lab sessions will be at least 24 hours apart to minimize carryover nicotine effect between sessions. In each experimental session, subjects will be randomly assigned to one of the five doses of nicotine (0.0125, 0.025, 0.05, 0.1 and 0.2 mg/70 kg or about 0.18, 0.36, 0.7, 1.4 and 2.8  $\mu$ g/kg). At the beginning of each experimental session, subjects will first sample the assigned nicotine dose and placebo (saline) condition that are randomly labeled as A or B. Beginning 15 minutes after the second sample dose, subjects will have the opportunity to choose between drug A or B every 15 minutes, for a total of ten opportunities over a 165-minute period. Immediately after subjects make their choice, drugs will be administered over 30 seconds using an infusion pump. The main outcome measure will be the number of nicotine self-administrations for each nicotine dose. The parameters of this nicotine self-administration procedure were based on our previous study (Sofuoglu et al. 2008a).

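### Post-hoc and secondary tests: Holm's step-down procedure would replace plain Bonferroni at the same 5% family-wise level and lose no rejection

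*Combined protocol and SAP*

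**What the plan says.** The first paragraph of section 12 sets two rules. For the principal questions, "Significance level of 0.05 will be used for the main hypotheses". For the rest, "Bonferroni correction will be applied for post-hoc tests and secondary analyses". Neither Holm nor any other step-down procedure is mentioned. The section does not list the tests in the corrected family, state how many there are, or give an adjusted alpha.

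The Aim #1 analysis "will compare the proportion of NSAs at each dose to 0.5 across subject groups", and the Aim 2 analysis takes a similar approach to the subjective ratings. Under Rationale for sample size the plan says "With our sample of 72 subjects we can detect such a proportion (67%) as statistically different from 50% with 80% power". The level behind that figure is 0.05, two-sided. For Aim 2 it says that "we can detect medium effects ( $d'=0.34$ ) for the threshold tests" on the same assumptions. That paragraph makes no multiplicity adjustment.

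**The concern.** An unqualified Bonferroni correction is normally understood as the single-step rule: every test in a family of m is judged at 0.05/m, however many of the others have already been rejected. Holm relaxes the limit after each rejection without exceeding the same family-wise level. Wherever a family contains more than one real effect, the single-step rule therefore forgoes some power.

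The plan expects nicotine choice to rise over the lower doses and flatten at the higher ones. Clear and marginal effects could then sit in the same family, which is a setting where Holm helps. What is at stake is some missed post-hoc or secondary findings in a study limited to 72 completers. The validity of the results is not at stake.

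**Working it through.** **1. The plan's own figures.** Inputs from Rationale for sample size: n = 72, two-sided alpha 0.05, 67% (two-thirds) against 50%, and d = 0.34.

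- Aim 1, exact binomial with one binary unit per subject: reject at 45 or more of 72 (upper-tail probability 0.0222). Power is 0.810 at 2/3 and 0.826 at 0.67.
- Aim 2, one-sample t test: noncentrality 0.34 × √72 = 2.885. Power is 0.812.

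The stated 80% reproduces, at unadjusted alpha. It does not depend on the Bonferroni clause.

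**2. The two rules.** Bonferroni rejects test i if p_i ≤ 0.05/m. Holm orders the p-values and rejects p_(k) while p_(k) ≤ 0.05/(m − k + 1), stopping at the first failure. For m = 5 the Holm limits are 0.0100, 0.0125, 0.0167, 0.0250 and 0.0500, against 0.0100 throughout for Bonferroni.

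- No Holm limit is below 0.05/m, so every Bonferroni rejection is kept.
- The first limit is the same, so the chance of at least one rejection is the same.
- With m0 true nulls, the first true null to be rejected faces a limit of at most 0.05/m0. The family-wise error is then at most m0 × 0.05/m0 = 0.05, whatever the dependence.

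**3. What Bonferroni costs at the plan's d = 0.34.** By noncentral t with n = 72, power per test is 0.812 unadjusted, 0.723 at m = 2, 0.595 at m = 5 and 0.499 at m = 10.

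**4. What Holm recovers, m = 5 (assumed).** Simulation with 200,000 replicates, z statistics with mean d√72, and d = 0.34 for each real effect. The normal approximation puts Bonferroni power at 0.62, a little above the t-based 0.595. Average power per real effect:

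| Real effects | Independent: Bonferroni → Holm | Correlation 0.5: Bonferroni → Holm |
|---|---|---|
| 1 | 0.622 → 0.624 | 0.622 → 0.622 |
| 3 | 0.621 → 0.664 | 0.620 → 0.657 |
| 5 | 0.622 → 0.740 | 0.621 → 0.720 |

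With all five effects real and tests independent, the chance of rejecting all five goes from 0.093 to 0.343. The chance of at least one rejection stays at 0.992. With all nulls true, family-wise error is 0.049 for both methods (0.042 at correlation 0.5). With all effects real and independent, the average goes from 0.740 to 0.801 at m = 2 and from 0.531 to 0.652 at m = 10.

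**5. Two assumed families of ten tests.** n = 72, t tests, 20,000 simulated trials, limit 0.05/10 = 0.005 against Holm.

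- (a) Two questionnaire items at five doses, standardised effects 0.05, 0.15, 0.30, 0.45 and 0.60, correlations 0.3 to 0.6. Power at 0.30 goes from 37% to 45–46%, and at 0.45 from 82% to about 86%. At 0.15 it goes from 6% to 10%, and at 0.05 from 1% to 2%.
- (b) Ten pairwise dose contrasts with nicotine choice of 50, 53, 60, 67 and 67%. At SD 0.22, power for 50 against 60% goes from 44% to 52%, and the average over true differences from 50% to 54–55%. At SD 0.28 the average goes from 35% to 38%.

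Across these, gains on middle-sized effects and averages run from 3 points (35 to 38) to 9 points (37 to 46). With all nulls true, family-wise error is about 4% for both methods.

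**6. Error use when some nulls are true.** In family (a) with the two lowest doses truly null (effects 0, 0, 0.30, 0.45, 0.60), the chance of any false rejection at those doses is about 1.9% with Bonferroni and 3.4% with Holm. Both are inside the 5% limit.

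**The case against.** The strongest objection is that Bonferroni is valid, prespecified and conservative, and that a preference for Holm could be voiced about almost any plan that names Bonferroni. That stands as to weight: this is not an error. It does not remove the point, because the gain follows for any family and the change is one phrase.

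Three stronger readings are tempting, and the documents do not support them.

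- **That Bonferroni weakens the search for the lowest active dose.** The threshold tests belong to Hypotheses 1A and 2A. Section 12 appears to test these as main hypotheses at 0.05, and the sample-size paragraph powers them at unadjusted 0.05. On that reading Holm changes nothing for the thresholds. The plan is not fully explicit here, but it does not place those tests under the Bonferroni clause.
- **That the families in step 5 are the plan's families.** No Bonferroni family is listed. Family (a) closely resembles the Hypothesis 2A analysis, which may fall outside the clause. Pairwise dose contrasts are not prescribed for this trial; dose-against-dose post-hoc comparisons appear only in the report of the preliminary study.
- **That Bonferroni buys no error control at all.** A check with all nulls true cannot show this, because the two methods have the same family-wise error there by construction. With some nulls true, Bonferroni makes fewer false rejections (step 6). Holm uses more of the error that the plan already permits.

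It also stands that very small effects remain almost undetectable under either method, and that Holm, like Bonferroni, cannot be applied until the family is listed. That gap matters more than the choice between the two.

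**Conclusion.** The point holds as an optional efficiency gain for the tests governed by the Bonferroni clause, and for those only. That Holm keeps every Bonferroni rejection and holds the same 5% family-wise limit is a mathematical result and needs no assumption about this trial.

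The size does need assumptions. In assumed families of ten tests with 72 subjects it is roughly 3 to 9 points of power on middle-sized effects. In an assumed family of five with equal effects it runs from about 0 to 12 points per test, depending on how many effects are real. It is close to nil when only one is real, and the chance of at least one rejection is unchanged. The actual gain cannot be computed, because family size, effects, standard deviations and correlations are not given. The main-hypothesis alpha, the target of 72 completers and the stated 80% power are unaffected.

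**What to change.** In the first paragraph of section 12, replace the words Bonferroni correction with Holm step-down Bonferroni correction for the post-hoc tests and secondary analyses. Make the change before unblinding.

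It needs no further subjects, data or assumptions. There are two costs. Holm has no equally simple simultaneous confidence intervals; Bonferroni or unadjusted intervals, labelled as such, can be shown beside the Holm-adjusted p-values. And Holm spends more of the allowed 5% when some nulls are true, as in step 6. If the sponsor values matching intervals or the extra conservatism above the added power, keeping Bonferroni is defensible.
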